**Table 1 Objectives and Corresponding Endpoints**

Safety Objective (Primary Study Objective)	Corresponding Endpoints
• To evaluate the safety and tolerability of escalating doses of DHES0815A administered by IV infusion every 3 weeks to patients with advanced or metastatic HER2-positive BC including estimation of the MTD, determination of the RP2D, and characterization of DLTs	

Occurrence and severity of adverse events including DLTs, with severity determined according to NCI CTCAE v4.0

Change from baseline in targeted vital signs

Change from baseline in targeted clinical laboratory test results, including ECGs

Number of cycles received and dose intensity

LVEF as assessed by ECHO or MUGA scan

Pharmacokinetic Objective	Corresponding Endpoint
• To characterize the DHES0815A pharmacokinetics when administered by IV infusion	

Concentration of three key PK analytes of DHES0815A (i.e., DHES0815A Total Antibody, acPBD-MA, and unconjugated PBD-MA, see Section 6.5) at specified timepoints

PK parameters of DHES0815A Total Antibody, acPBD-MA, and unconjugated PBD-MA

Activity Objective	Corresponding Endpoints
• To make a preliminary assessment of the anti-tumor activity of DHES0815A	

Objective response, defined as a complete response or partial response on two consecutive occasions <math>\geq 4</math> weeks apart, as determined by the investigator according to RECIST v1.1

Duration of response, defined as the time from the first occurrence of a documented objective response to disease progression or death from any cause, whichever occurs first, as determined by the investigator according to RECIST v1.1

Immunogenicity Objective	Corresponding Endpoints

 
To evaluate and characterize the immunogenic response to DHES0815A (by measuring anti-DHES0815A antibodies) administered by IV infusion, including the potential effects of ADAs on other outcome measures
 
	
 
Incidence of ADA formation to DHES0815A (anti-DHES0815A antibodies) during the study relative to the prevalence of ADA at baseline
 
Relationship between ADA status and safety, PK, biomarkers, or preliminary efficacy endpoints
 

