Patients in this study will be initially assessed for eligibility during the screening period (lasting  $\leq$  28 days). Following confirmation of eligibility, patients will receive DHES0815A by IV infusion on the first day of every cycle. A detailed PK evaluation will be performed during Cycle 1 and more limited PK assessments thereafter. Patients will be evaluated weekly by physical examination and by blood collections for routine hematologic and metabolic laboratory assessments for the first four cycles of DHES0815A treatment during dose escalation, the first two cycles during dose expansion, and less frequently thereafter. Cardiac ejection fraction (left ventricular ejection fraction [LVEF]) will be monitored by transthoracic echocardiogram (ECHO) or multiple-gated acquisition scan (MUGA) at baseline and in the last week (Days 15–21) of Cycles 1, 2, 4, and 6, and then after every four cycles thereafter. Ophthalmic examinations (best corrected visual acuity [BCVA] and anterior segment slit lamp examination with fluorescein) to monitor for visual and/or corneal changes will occur at baseline and during the last week (Days 15–21) of Cycles 2, 4, and 6, and every four cycles thereafter. Tumor assessment will occur at baseline and during the last week (Days 15–21) of every even-numbered cycle until Cycle 8 (i.e., at Cycles 2, 4, 6, and 8) and at every three cycles thereafter (i.e., at Cycles 11, 14, 17, etc.) until discontinuation or study termination.

Adverse events will be graded according to the National Cancer Institute Common Terminology Criteria for Adverse Events, Version 4.0 (NCI CTCAE v4.0). Patients deriving clinical benefit may be offered continued treatment with DHES0815A until disease progression or intolerable toxicity at the discretion of the investigator (see Section 3.1.1.4).

Disease status will be assessed using the Response Evaluation Criteria in Solid Tumors, Version 1.1 (RECIST v1.1) (Eisenhauer et al. 2009; see [Appendix 3](#)). Tumor status will be categorized as a complete response (CR), partial response (PR), stable disease, or progressive disease (PD), per RECIST v1.1. Objective response should be confirmed by repeat physical examination or image-based evaluation  $\geq$  4 weeks after the initial documentation, per RECIST v1.1 (see [Appendix 3](#)).

Blood samples will be collected for assessment of molecular and genetic biomarkers at baseline and end of study.

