### **4.6 TREATMENT, PATIENT, STUDY, AND SITE DISCONTINUATION**

#### **4.6.1 Study Treatment Discontinuation**

Patients must permanently discontinue study treatment if they experience any of the following:

- Any medical condition that the investigator or Sponsor determines may jeopardize the patient's safety if he or she continues to receive study treatment
- Investigator or Sponsor determines it is in the best interest of the patient
- Pregnancy
- Use of an anti-cancer therapy other than DHES0815A
- Symptomatic deterioration attributed to disease progression
- Confirmed disease progression per investigator assessment according to RECIST v1.1 unless a patient continues to demonstrate signs and symptoms of clinical benefit from DHES0815A treatment that is independent of RECIST v1.1, as judged by the investigator and upon discussion with the Medical Monitor (see [Appendix 3](#))

The primary reason for study treatment discontinuation should be documented on the appropriate eCRF. Patients who discontinue study treatment prematurely will not be replaced unless enrolled in the dose-escalation cohorts and they discontinue prior to completion of the 21-day DLT window.

Patients will return to the clinic for a treatment discontinuation visit within 42 days after the last dose of study drug (see [Appendix 1](#) for additional details).

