#### **4.6.2 Patient Discontinuation from Study**

Patients will return to the clinic for a study discontinuation visit at treatment discontinuation.

Patients have the right to voluntarily withdraw from the study at any time for any reason. In addition, the investigator has the right to withdraw a patient from the study at any time. Reasons for withdrawal from the study may include, but are not limited to, the following:

- Patient withdrawal of consent
- Study termination or site closure
- Patient non-compliance, defined as failure to comply with protocol requirements as determined by the investigator or Sponsor

Every effort should be made to obtain information on patients who withdraw from the study. The primary reason for withdrawal from the study should be documented on the appropriate eCRF. If a patient requests to be withdrawn from the study, this request must be documented in the source documents and signed by the investigator. Patients who withdraw from the study will not be replaced.

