## **6.6 ACTIVITY ANALYSES**

Objective response will be summarized by dose level and cohort. Objective response is defined as a CR or PR, as determined by investigator assessment according to RECIST v1.1 and confirmed by repeat assessment  $\geq 4$  weeks after initial documentation. Patients with missing baseline or no response assessments will be classified as non-responders.

Among patients with an objective overall response, duration of response (DOR) will be defined as the time from the initial CR or PR to the time of disease progression or death, whichever occurs first. If a patient has not experienced disease progression or death, DOR will be censored at the day of the last tumor assessment showing no disease progression.

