### Schedule of Activities (cont.)

- d Patients who have not withdrawn consent or been lost to follow-up will be contacted 42 days after the last dose of study drug for information on adverse events and initiation of any subsequent anti-cancer therapies.
- e Medical history includes all clinically significant diseases, surgeries, cancer history (including prior cancer therapies and procedures), reproductive status, smoking history, and all medications used by the patient within 7 days preceding the screening visit (including prescription drugs, over-the-counter drugs, and herbal/homeopathic remedies and therapies). Demographic data includes age, sex, and self-reported race/ethnicity.
- f Complete physical examination should include evaluation of head, eyes, ears, nose, and throat, and the cardiovascular, dermatologic, musculoskeletal, respiratory, gastrointestinal, genitourinary, and neurologic systems.
- g Limited physical examination should include systems of primary relevance (i.e., cardiovascular, respiratory, and any system that might be associated with tumor assessment) and systems associated with symptoms. Patients should be evaluated weekly by limited physical examination through Cycle 4, on Day 1 and Day 8 Cycles 5–8, and at least on Day 1 of each Cycle beyond Cycle 8.
- h Vital signs include measurement of respiratory rate, heart rate, systolic and diastolic blood pressure while the patient is in a seated position, pulse oximetry, and temperature. On Day 1 of Cycle 1 and on Day 1 of Cycle 2, and on the day of infusion where a 2-hour post-infusion observation period is warranted (Section 4.3.2), vital signs will be assessed prior to infusion, every 15 ( $\pm$  5) minutes during infusion, at the end of infusion ( $\pm$  5 minutes), and every 30 ( $\pm$  10) minutes after the infusion for 2 hours. For all other days of infusion where a 30-minute post-infusion observation period is allowed, vital signs will be assessed prior to infusion, every 15 ( $\pm$  5) minutes during infusion, at the end of infusion ( $\pm$  5 minutes), and at 30 ( $\pm$  10) minutes after infusion. Oxygen saturation via pulse oximetry will be monitored at a minimum every 15 ( $\pm$  5) minutes during infusion from pre-treatment to the end of the observation period.

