- m Tumor assessments should be performed at screening, during the last week (Days 15–21) of every even-numbered cycle until Cycle 8 (i.e., at Cycles 2, 4, 6, and 8) and every three cycles thereafter (i.e., at Cycles 11, 14, 17, etc.) until treatment discontinuation, and at study discontinuation visit (unless last prior tumor assessment was performed  $\leq$  4 weeks). Response should be assessed on the basis of physical examinations and image-based evaluations, using RECIST v1.1. CT scans should include the chest, abdomen, and pelvis; CT scans of the neck should be included if clinically indicated. MRI may be used instead of CT scans in patients for whom CT scans are contraindicated or in circumstances in which MRI is the preferred imaging modality. The same method of assessment and the same technique should be used at baseline and for all on-study assessments.
- n Please see [Appendix 2](#) for a complete list of PK and ADA blood draws.
- o Hematology consists of complete blood count, including hemoglobin, hematocrit, platelet count, RBC count, WBC count, and absolute differential count for neutrophils and lymphocytes; percentage or absolute count is acceptable for all other cell types (e.g., eosinophils, monocytes, basophils, bands, and other cells).
- p Serum chemistry includes sodium, potassium, chloride, bicarbonate, glucose, BUN or urea, creatinine, calcium, phosphorus, magnesium, total and direct bilirubin, total protein, albumin, LDH, ALT, AST, and ALP.
- q ECHO or MUGA scans to monitor LVEF should be conducted during screening, at the end of the DLT window (i.e., end of Cycle 1), during the last week (Days 15–21) of even-numbered cycles until Cycle 6 (i.e., at Cycles 2, 4, and 6), every four cycles thereafter (i.e., at Cycles 10, 14, 18, etc.), and at the study discontinuation visit (unless no study drug has been given since the last ECHO or MUGA scan). Other assessments should be conducted if clinically indicated.

## Appendix 1

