### **Appendix 3 Response Evaluation Criteria in Solid Tumors (RECIST): Modified Excerpt from Original Publication (cont.)**

Patients with a global deterioration of health status requiring discontinuation of treatment without objective evidence of disease progression at that time should be reported as “symptomatic deterioration.” Every effort should be made to document objective progression even after discontinuation of treatment. Symptomatic deterioration is not a descriptor of an objective response; it is a reason for stopping study therapy. The objective response status of such patients is to be determined by evaluation of target and non-target disease as shown in Tables 1–3.

For equivocal findings of progression (e.g., very small and uncertain new lesions; cystic changes or necrosis in existing lesions), treatment may continue until the next scheduled assessment. If at the next scheduled assessment, progression is confirmed, the date of progression should be the earlier date when progression was suspected.

In studies for which patients with advanced disease are eligible (i.e., primary disease still or partially present), the primary tumor should also be captured as a target or non-target lesion, as appropriate. This is to avoid an incorrect assessment of complete response if the primary tumor is still present but not evaluated as a target or non-target lesion.

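### A responder who stops for symptomatic deterioration without RECIST progression is censored for duration of response as if still responding, and almost no follow-up after treatment can correct this

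*Combined protocol and SAP*

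**What the plan says.** **Endpoint.** Table 1 gives "Duration of response, defined as the time from the first occurrence of a documented objective response to disease progression or death from any cause", as determined by the investigator under RECIST v1.1.

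**Scans.** Section 3.1 continues them "and at every three cycles thereafter (i.e., at Cycles 11, 14, 17, etc.) until discontinuation or study termination". Appendix 1, footnote m, is more specific: scans run "until treatment discontinuation, and at study discontinuation visit (unless last prior tumor assessment was performed", the exception being a scan in the preceding 4 weeks. Section 4.6.2 fixes the timing of that visit: "Patients will return to the clinic for a study discontinuation visit at treatment discontinuation". Footnote c allows up to 42 days after the last infusion, or until a new regimen if that comes first.

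**Later contact.** Under footnote d, patients "will be contacted 42 days after the last dose of study drug for information on adverse events and initiation of any subsequent anti-cancer therapies". Sections 5.3.1 and 5.3.5.8 require all deaths to be reported within the adverse event period, which closes at 42 days or earlier, for example at a new anti-cancer therapy. After that, Section 5.6 asks only for serious events believed to be drug-related.

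**Analysis.** Section 6.6 states that, without progression or death, "DOR will be censored at the day of the last tumor assessment showing no disease progression". Section 6 limits the final analysis to data up to patient or study discontinuation.

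**Symptomatic deterioration.** Section 4.6.1 lists "Symptomatic deterioration attributed to disease progression" among the reasons for permanent discontinuation. Appendix 3 says it is a reason to stop therapy and not a response category. Section 6.6 does not mention it.

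**The concern.** The endpoint runs to progression or death, but systematic data collection ends around the time treatment stops. A responder who stops without RECIST progression is censored at the last scan that showed none. Standard survival methods then assume that this patient's later risk matches that of responders still under observation.

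For symptomatic deterioration that assumption contradicts the recorded reason for stopping. The investigator has judged that the disease is progressing, yet the analysis treats the patient as an ongoing response. Each such case removes an event and lengthens the estimated DOR.

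DOR is one of the two activity endpoints. Section 3.1.1.3 lists activity among the data that inform the recommended Phase II dose, so a reader needs to know what the reported duration measures.

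**Working it through.** **What can be reproduced.** The documents give no DOR figure, event count or estimator. The nearest activity figure is in Section 6.1.2: 10 responders of 25, 40%, with an 80% CI of 27% to 55%. The exact (Clopper-Pearson) limits are the 10% quantile of Beta(10, 16) and the 90% quantile of Beta(11, 15), which give 26.5% and 54.8%. This agrees. It concerns the response rate only.

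**Step 1. Who is censored.** A responder who stops without RECIST progression has one further chance of a documented progression, the closing scan, and a window of at most 42 days for a recorded death. The patient is censored if the closing scan is waived or shows no progression and no death falls in the window. Later events are not systematically collected.

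**Step 2. Symptomatic deterioration.** Assumptions: exponential DOR with hazard λ; a Kaplan-Meier-type estimate; a share f of progressions censored just before they would be recorded, with the same timing as the rest.

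- Hazard seen by the analysis: (1−f)λ.
- True median: ln 2/λ. Estimated median: ln 2/[(1−f)λ]. Ratio: 1/(1−f).

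| f (assumed) | 1/(1−f) | Median if the true value is 6 months (assumed) |
|---|---|---|
| 2% | 1.02 | 6/0.98 = 6.1 |
| 5% | 1.05 | 6/0.95 = 6.3 |
| 10% | 1.11 | 6/0.90 = 6.7 |

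With 10 responders, the number in the plan's own example, one such patient among ten progressions already means f = 10%. Scans are 2 × 3 = 6 weeks apart and later 3 × 3 = 9 weeks apart, so an actual estimate would move in jumps. The table gives the underlying shift.

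**Step 3. Stops for toxicity.** Assumptions: λ = ln 2/6 per month; a share p of responders stops before progression; the progression hazard after stopping is kλ. Censoring at the stop leaves the Kaplan-Meier median at 6.0 months whatever k is. The median with complete follow-up was obtained by simulation (2,000,000 draws).

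| p | k | Median, complete follow-up | 6.0 / that median |
|---|---|---|---|
| 15% | 0.5 | 6.22 | 0.96 |
| 15% | 1 | 6.01 | 1.00 |
| 15% | 2 | 5.74 | 1.05 |
| 15% | 3 | 5.58 | 1.08 |
| 30% | 0.5 | 6.53 | 0.92 |
| 30% | 1 | 6.00 | 1.00 |
| 30% | 2 | 5.44 | 1.10 |
| 30% | 3 | 5.12 | 1.17 |

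The sign depends entirely on k, which the documents do not give.

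**Step 4. Scale against sampling error.** With d = 10 events, the exponential 80% interval for the median runs from 2d/χ²(0.90; 2d) to 2d/χ²(0.10; 2d) times the estimate, that is 0.70 to 1.61. The shifts in Step 2 lie well inside this.

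**The case against.** The best defence is that the protocol already narrows the gap.

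- Section 4.5.5 calls for an unscheduled scan whenever clinical or laboratory findings suggest progression during treatment, with no 4-week waiver. Deterioration that leads to stopping will usually arise in that phase.
- Section 5.3.5.10 describes clinical progression as rare and asks for objective documentation. Appendix 3 extends this: "Every effort should be made to document objective progression even after discontinuation of treatment".
- Deaths up to Day 42, including deaths from breast cancer, are recorded and count as events unless the reporting period has closed earlier.
- DOR is descriptive in a Phase I safety trial. No estimator is named, Section 6 allows listings when numbers are small, and no numerical escalation or stopping rule uses DOR.

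Most of this stands, and it points to a small f. It does not close the gap. The unscheduled scan may not meet RECIST criteria for progression. The Appendix 3 request has no visit or window behind it, and progression documented after discontinuation may fall outside the Section 6 data cut. Once a responder with clinical deterioration reaches the analysis without RECIST progression or a recorded death, Section 6.6 leaves no choice but to censor.

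A reader might also infer that responders who stop for toxicity bias DOR upward, and more so at higher doses. The documents do not support that. They give no progression hazard after stopping, and Step 3 shows no bias if the hazard is unchanged and a downward bias if it falls.

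**Conclusion.** The mismatch between the DOR definition and the data collected for it is documented. For responders stopped for symptomatic deterioration without RECIST progression or a recorded death, censoring is informative and lengthens a Kaplan-Meier-type DOR by 1/(1−f). On assumed shares this is +2% to +5% at 2% to 5%, and +11% at 10%. The protocol's own wording favours the low end, although one patient in ten responders reaches the higher figure. The result rests on exponential DOR and Kaplan-Meier-type handling, which the censoring rule implies but Section 6.6 does not name.

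Two stronger readings should be set aside. Tumor assessment does not simply cease when treatment stops, because Appendix 1 provides a closing scan. Nor is DOR shown to be biased upward overall, because the direction for toxicity stops is unknown. The definitions of DLT, MTD and objective response are untouched. This is an inexpensive improvement to a secondary, descriptive analysis.

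**What to change.** **In Section 6.6:**

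- Add a supplementary DOR analysis that counts discontinuation for symptomatic deterioration attributed to progression as an event, reported beside the RECIST-only analysis. Section 4.6.1 already requires the primary reason for discontinuation on an eCRF. Confirm that the form has this category.
- Describe the RECIST-only DOR as essentially an on-treatment quantity.

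**Optional.** For responders who stop without progression, record the dates of progression (from standard-of-care imaging), new anti-cancer therapy and death until study end. The Section 6 data cut must then be amended, or these data may not enter the final analysis.

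**Cost.** The supplementary analysis is minor extra work and may give a shorter reported DOR. The optional follow-up adds a few eCRF fields and some site effort. Its irregular scan timing would make progression dates less precise, so it is the more debatable part.

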### **3.1.1 Dose-Escalation Stage**

Approximately 24–30 patients will be enrolled in the dose-escalation stage. Cohorts of 3–6 patients each will be treated at escalating doses of DHES0815A in accordance with the dose-escalation rules described below. The starting dose of DHES0815A is based on nonclinical safety assessments and will be no higher than 0.6 mg/kg IV Q3W (see Section 3.3.2 for more details). For added safety during dose escalation, treatment will be staggered such that the first patient treated at each dose level will receive his or her first infusion at least 1 day prior to subsequent patients in that cohort. In addition, cohorts may be expanded even in the absence of dose-limiting toxicities (DLTs) in order to evaluate non-DLT adverse events further or to collect additional safety or PK data. Intrapatient dose escalation as per Section 3.1.1.3 will be allowed.

Patients will be closely monitored for adverse events during the DLT assessment window, defined as Days 1–21 of Cycle 1. Adverse events identified as DLTs, as defined in Section 3.1.1.1, will be reported to the Sponsor within 24 hours (see Section 5.3.1).

Patients who discontinue from the study prior to completing the DLT assessment window for reasons other than a DLT will be considered non-evaluable for dose-escalation decisions and maximum tolerated dose (MTD) assessments and will be replaced by an additional patient at that same dose level. Patients who receive supportive care during the DLT assessment window that confounds the evaluation of DLTs may be replaced at the discretion of the Medical Monitor.

